4.2. Adverse Event Data Collection and Documentation

Data Collection: In addition to a medical history, clinical laboratory data will also be collection at enrollment. Following enrollment, information will then be collected on any new adverse event that occurs within 30 days following study visit procedures.

Documentation: Information on adverse events will be recorded on study visit CRFs (through the online REDCap interface). An assessment will be made by study investigators with respect to the severity grade and relationship of the AE to study participation (see 4.2 below).

Additional information ascertained for each adverse event includes: a) date of onset, b) relationship to study participation (see section 4.3 below), c) any action taken on study procedures, d) the outcome of the adverse event (e.g., resolved or ongoing), and e) whether the adverse event qualifies as a serious adverse event (including the SAE criteria fulfilled).

A narrative is required and is to be included in source documentation for all serious adverse events, as well as any other untoward events involving risks to participants that is unanticipated or unexpected and are reasonably believed to be related to research participation. The circumstances surrounding these events should be reported using the serious adverse event CRF, and reviewed with the principle investigator as soon as the event is known.

NOTE: *information on adverse event do NOT need to be reported if \leq grade 2.*

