2. METHODOLOGY

2.1. Trial Design

We propose to evaluate the feasibility, acceptability and preliminary impact of *PrEP iT!* using a randomized controlled trial (RCT) study design. Young men who have sex with men (YMSM) recently (re)initiating PrEP will be randomized to receive either *PrEP iT!* plus usual care or usual care alone, and followed for 6 months. Assessments and study data collection will occur at entry ('baseline'), and then again at 3-and 6-months in-person or online via an online HIPPA-complaint teleconferencing platform such as Zoom. A total sample size of n=80 participants will be enrolled in this pilot study phase.

The purpose of this pilot study phase is to inform the development of a subsequent clinical trial to more definitely establish the potential benefit of the *PrEP iT!* mobile intervention. A RCT study design was chosen to most closely mimic the procedures and process of the larger efficacy trial by identifying unforeseen challenges.

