2.7. Study Visit Procedures

Study candidates, whether referred by PrEP clinic staff or self-referred from recruitment materials, will be assessed for potential eligibility through a self-directed online screening survey, or through research staff who can assess eligibility by telephone or by assisted participants with completing the online survey. All interested candidates will then undergo a study visit, during which their eligibility will be confirmed followed by informed consent. After consent procedures, participants will complete a computer-assisted baseline survey and complete enrollment visit procedures.

After enrollment, participants are randomized 1:1 to either the intervention (PrEP iT! + usual care) or control (usual care) arm. All participants will be provided usual PrEP educational information encouraged to attend their regular healthcare visits. Participants randomized to the intervention arm will be guided through setting up their user account and user profile, provided with basic training on how to navigate and use intervention components, and given the opportunity to ask questions.

Both control and intervention participants will be offered an optional blood draw at their enrollment and 6 visits. Blood samples and the information collected may be used by the study sponsor, its research partners or companies for additional testing of Tenofovir and metabolites. At the end of this study, these samples may be held in storage by Hennepin Healthcare Research Institute for up to 20 years. After 20 years, the samples will be destroyed. Participants can request that their samples be destroyed at any time by writing to investigators.

YMSM will undergo a follow-up assessment at both 3- and 6-month visits. The follow-up visits include ascertainment of clinical information that was conducted as part of usual PrEP care (e.g., repeat testing for HIV and other STIs), completion of a computerized survey assessment, and collection of a dried blood spot specimen for the TFV-DP analyses. If visit is in person, a finger prick will be done to collect several drops of blood. If visit is online, a self-collection kit will be mailed to participants home where they collect blood by pricking their finger, and then mailing the blood sample to a lab in a pre-paid mailer. See Clinical Management below for procedures for procuring care for diagnoses or disease events that are identified during study conduct.

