A complete list of study visit procedures, data collection, and evaluations performed at Screening, Enrollment and/or Follow-up study visits is listed below in **Table 2**.

Table 2: Study Visit Procedures and Evaluations

Measure	Screening Assessment	Enrollment Visit	3 Month Visit	6 Month Visit
RCT online screener	X			
Informed Consent		X		
Verification of eligibility		X		
Randomization		X		

Participant and clinical data				
Demographic information	X			
HIV status	X	X	X	X
PrEP medications and strategy		X	X	X
Medical history		X	X	X
Clinical labs		X	X	X
Disease or clinical events		X	X	X
Surveys Items/Scales				
Demographics and Baseline Characteristics		X		
Technology Use Questions		X	X	X
eHealth Literacy		X	X	X
HIV Negative Cascade		X	X	X
U=U Questions		X	X	X
Substance Use		X	X	X
Sexual Risk Behavior		X	X	X
Mental Health		X	X	X
Social Support		X	X	X
Technology Use Questions			X	X
Intervention Acceptability			X	X
Exit Interview				X
Specimen collection				
Dried Blood Spot Collection		X	X	X
Blood for Storage		X		X

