4.3. Relationship to Study Participation

For all adverse events that occur within 30 days of study visit procedures, study investigator(s) will assess the potential relationship of the event to the study and designate one of the following:

- i. **Definitely or Probably Related:** the adverse event is reasonably related in time, and the adverse event is more likely, or definitely, explained by study participation than other causes.
- ii. **Possibly Related.** The adverse event is reasonably related in time, and the adverse event could be explained by the study or equally well by causes other than study participation.
- iii. **Not Related.** The adverse event is clearly explained by an alternative explanation not related to study participation.

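### Adverse-event collection is tied to the 30 days after each visit, which covers about one third of a 6-month follow-up with continuous app use and conflicts with other safety rules in the protocol

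*Combined protocol and SAP*

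**What the plan says.** Section 4.2 sets the collection rule: following enrollment, "information will then be collected on any new adverse event that occurs within 30 days following study visit procedures". Section 4.3 opens the causality assessment with a similar limit: "For all adverse events that occur within 30 days of study visit procedures, study investigator(s) will assess the potential relationship". A note at the end of 4.2 adds that "information on adverse event do NOT need to be reported if" the grade is 2 or lower.

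The exposure has a different rhythm. Under 2.1, participants "will be randomized to receive either *PrEP iT!* plus usual care or usual care alone, and followed for 6 months". Section 2.7 sets up the app at the enrollment visit ("Participants randomized to the intervention arm will be guided through setting up their user account and user profile") and then schedules only two further contacts: "YMSM will undergo a follow-up assessment at both 3- and 6-month visits". Section 2.5 describes daily self-monitoring and text messages in between.

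Other safety text is wider than the 30-day rule:
- 4.1 treats any worsening of a preexisting condition after enrollment as an adverse event, with no time limit.
- 4.2 itself requires a narrative and the serious-event form for every serious event, and for other untoward events that are unexpected and reasonably believed related. It states no window and no grade floor for these. It also lists relationship among the items recorded for each adverse event.
- 4.4 has investigators review all documented events weekly, including their relationship to participation. Serious, unexpected events that are at least possibly related go to the IRB within 2 working days of knowledge; unrelated serious events go into periodic reports.
- Table 2 has a row for "Disease or clinical events" at enrollment, 3 and 6 months, with no look-back period.

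**The concern.** A 30-day window after a visit suits a procedure done at that visit, such as a finger prick or blood draw. It does not suit an app and text programme used between visits. A harm from the app or messages has no reason to be confined to the month after a visit.

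The rule also works oddly at the visits themselves. At the 3-month visit (day 90), a non-serious grade 3 event on day 20 qualifies for collection, while one on day 85 does not. At stake is whether the adverse-event record of this pilot, which is meant to inform a larger trial, describes the period of use or mainly the months after visits. Staff would also hold conflicting instructions for a serious event in a gap.

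**Working it through.** The plan states no coverage figure, so there is none to reproduce. The check counts days.

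**Inputs.** Window: 30 days after each visit (4.2). Visits: enrollment, 3 and 6 months (2.1, 2.7, Table 2). Follow-up: 6 months (2.1). Start of app use: enrollment visit (2.7). Assumption: app use lasts through month 6, since no end date for access is given. Exact visit days and allowed deviations are not stated, so several timings are tried.

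**Formula.** Covered share = days of follow-up lying in any window [visit, visit + 30) ÷ total days of follow-up.

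**Base case.** With visits at days 0, 90 and 180, the windows are days 0–30, 90–120 and 180–210. The third lies wholly after follow-up and adds no covered follow-up time. Covered: 30 + 30 = 60 days; 60/180 = 33.3%. Outside: 120/180 = 66.7%.

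| Assumed timing | Visit days | Covered | Outside |
|---|---|---|---|
| 30-day months | 0, 90, 180 | 60/180 = 33.3% | 66.7% |
| Calendar months | 0, 91, 182 | 60/182 = 33.0% | 67.0% |
| 12 and 24 weeks | 0, 84, 168 | 60/168 = 35.7% | 64.3% |
| Visits about 14 days early | 0, 76, 168 | 60/168 = 35.7% | 64.3% |
| Visits about 14 days late | 0, 104, 196 | 60/196 = 30.6% | 69.4% |
| 3-month visit missed | 0, 180 | 30/180 = 16.7% | 83.3% |

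**Reading 4.3 in both directions.** Its phrase, "For all adverse events that occur within 30 days of study visit procedures", does not say before or after. Read as 30 days either side, the windows are days 0–30, 60–120 and 150–180: 30 + 60 + 30 = 120 of 180 days, leaving 33.3% outside the relationship assessment. This does not help collection, because 4.2 counts forward only.

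**What happens to an event on day 60, by type:**
- *Non-serious, grade 3 or above, expected or not believed related:* outside the 4.2 window and outside the narrative rule, so no routine collection. Table 2 may bring it to light, but nothing links that row to the adverse-event record.
- *Non-serious, unexpected and believed related:* recorded through the narrative rule.
- *Serious:* narrative and form required under 4.2. Day 60 is 60 days after enrollment, so under 4.3 with a forward window it gets no relationship category. Section 4.2's list of recorded items and the weekly review in 4.4 both ask for one, and 4.4 needs it to choose between 2-day and periodic reporting.
- *Worsening of a preexisting condition:* an adverse event under 4.1, outside collection under 4.2.

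**The note on grade.** Seriousness in 4.1 turns on outcome, such as hospitalization, not on grade. A grade 2 event leading to hospitalization is therefore exempt under the note and mandatory under the narrative rule in the same section. A mild event that is related but anticipated falls under neither route. Unwanted disclosure may be an example: 2.5 keeps the texts generic for that reason. Whether it counts as anticipated depends on the consent form, which was not available for this review.

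**The case against.** The strongest reply is that the protocol has other routes. Serious events and unexpected related events are recorded whenever they occur and go to the principal investigator once known. IRB timing runs from knowledge of the event, with no 30-day limit. Medical history, clinical labs and clinical events are taken at 3 and 6 months, a mental health survey is given at both visits, an exit interview is held at month 6, and the medical record can be consulted (3.2). The intervention is an app in an 80-person pilot with feasibility and acceptability as primary outcomes, and PrEP itself is prescribed and managed in usual care.

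Much of this stands, and it rules out stronger readings that a reader might infer:
- *That two of every three events go unrecorded.* The two-thirds figure is follow-up time. Turning it into events needs a constant hazard and no capture outside the windows; the narrative rule contradicts the latter.
- *That IRB reports rest on one third of exposure.* The trigger in 4.4 is knowledge of the event, not its date.
- *That a comparison of safety between arms would be biased.* No such summary is planned: 2.6 lists no adverse-event outcome and 5.3 no adverse-event analysis.
- *That the period after the 6-month visit is lost exposure.* It lies beyond the 6 months. Table 2 simply shows no scheduled contact after it opens.

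What the reply does not answer is the mismatch itself. None of the wider passages sets a look-back period, or says that events outside the 30 days enter routine collection and the 4.3 assessment.

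**Conclusion.** The point holds as a mismatch between the collection rule and the exposure, together with an internal inconsistency. The 4.2 windows cover about 33% of follow-up (31% to 36% under the timings tried with both follow-up visits kept; 17% if the 3-month visit is missed). This rests on a literal reading of 4.2 and on app use through month 6.

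The practical gap is narrower than the uncovered time suggests. It concerns non-serious events of grade 3 or above that are not both unexpected and believed related, the missing relationship category for serious events between windows, and mild related events that are anticipated. Sections 4.2, 4.3 and the note need reconciling with 4.1, the narrative rule, 4.4 and Table 2. The intervention is low risk, so this should be corrected but does not threaten the trial's primary aims.

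**What to change.** - In 4.2 and 4.3, collect and assess adverse events from enrollment through the 6-month visit, asked as *since your last visit* at the existing 3- and 6-month visits. State that events found through the clinical-events row of Table 2 enter this process.
- Keep the 30 days after the 6-month visit for procedure-related events that are reported spontaneously or seen in the medical record. Blood spots and the optional stored blood are collected at that visit, so simply ending collection there would lose the one period the present rule suits.
- Limit the note's exemption to events of grade 2 or lower that are neither serious nor judged related to study participation.

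The cost is a wording change, a few more form entries and more unrelated events of grade 3 or above to review. No new visit or test is needed.

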4.3. Relationship to Study Participation

For all adverse events that occur within 30 days of study visit procedures, study investigator(s) will assess the potential relationship of the event to the study and designate one of the following:

- i. **Definitely or Probably Related:** the adverse event is reasonably related in time, and the adverse event is more likely, or definitely, explained by study participation than other causes.
- ii. **Possibly Related.** The adverse event is reasonably related in time, and the adverse event could be explained by the study or equally well by causes other than study participation.
- iii. **Not Related.** The adverse event is clearly explained by an alternative explanation not related to study participation.

4.4. Review and Reporting of Adverse Events

NOTE: All adverse events that are collected and documented, whether or not they are serious or related to study participation, are reviewed weekly by the study investigator(s) for determination of grade, severity, relationship to study participation, and need to refer for additional medical evaluation.

The SDSU IRB will receive safety reports for all adverse events that are: **serious and unexpected**. Time frame for reporting will be:

- i. Reports for serious adverse events that are definitely, probably, or possibly related to study participation will be sent within **2 working days** of knowledge of the event.
- ii. Serious adverse events not related to study participation will be reported as part of usual study reports at pre-specified intervals (e.g., bi-annually, annually).

Aggregate annual reports will also be created and submitted to the IRB, which will include information on unexpected adverse events or any unanticipated problem that poses risks to participants, and is believed to be related to research participation.

5. STATISTICAL METHODS

5.1. Sample Size Considerations

The sample size for this proof-of-concept study (n=40 per group; n=80 total) is consistent with recommendations of sample sizes for pilot studies of this nature.²² Power calculations are presented for the two adherence outcomes: TFV-DP levels and the adherence score. For the TFV-DP levels (n=20 in each arm), prior research suggests that approximately 40% will have levels TFV-DP levels >700 fmol/punch at 3 months. Assuming a type I error of 5% and using a chi-square test statistic, we have 80% power to detect a relative risk of 2.0 or larger (i.e., that the intervention group is 2.0 times as likely to have high levels of TFV-DP as the control group). Adherence may decrease by 6 months, increasing our detectable effect. If we assume 30% adherence at 6 months, we have 80% power to detect a relative risk of 2.4 or higher. For the adherence score derived from Wilson et al.'s²³ 3-item measure, prior research on ART therapy suggests a standard deviation of approximately 20.²³ Assuming we will see the same standard deviation among PrEP users and a type-1 error rate of 5%, we have 80% power to detect a difference in adherence scores of 12.7 units between the two groups. This is approximately half of a standard deviation change, and should provide good preliminary evidence to inform future trials.

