5.3. Analysis Plan

Feasibility of delivering the intervention will be assessed by examining the percentage of eligible people who are successfully recruited into the study and by the percentage of participants retained at each visit. Chi-square tests (or Fisher's exact test, for small cell counts) will be used to compare the intervention and control groups in the proportions of participants retained at both 3- and 6-month follow-up. We will use the following retention cut-off percentages to assess feasibility: a) 90+ = strong feasibility; b) 80-89% = acceptable feasibility; c) 70-79% = modest feasibility with a need for improvement; d) <70% = unacceptable feasibility.

Acceptability will be measured using a 10-item self-report System Usability Scale (SUS)²⁴ computed in the intervention arm over time (at 3- & 6-months). The average SUS score across 400 studies was 68²⁴ (possible range 0-100); therefore, an average score of ≥ 68 will be considered acceptable and ≥ 80 highly acceptable. We will estimate overall acceptability and changes over time. Acceptability will further be assessed by recording the frequency of *PrEP iT!* interaction (average number of uses per week) over follow-up time.

The preliminary impact of the mobile intervention will specifically be evaluated. We will focus on two adherence measures to estimate the preliminary efficacy of the *PrEP iT!* intervention. Objective adherence will be assessed via TFV-DP levels in DBS samples ($n \geq 20$ per treatment arm). TFV-DP data will be dichotomized into high levels (≥ 700 fmol/punch) vs low levels (< 700 fmol/punch) and the difference in proportion of high levels of TFV-DP between treatment arm will be estimated using chi-square or Fisher's exact test at both 3 and 6 months. In a separate analysis, we will keep TFV-DP as a continuous variable and examine differences between control and intervention groups using T-tests and permutation tests. Second, at 3 and 6 months, we will use the validated 3-item self-report adherence measure developed by Wilson and his colleagues.²³ T-tests will compare the mean adherence score between intervention and control arm at 3 and 6 months. Permutation tests will also be used to test for treatment group differences, since they do not require distributional assumptions and are typically more robust.

6. REFERENCES:

1. Centers for Disease Control and Prevention. HIV Surveillance Report, 2016. 2017.

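### Minor: at the printed bounds RR 2.0 and RR 2.4, the chi-square test named in Section 5.1 has about 75% and 76-78% power with 20 per arm, not the stated 80%

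*Combined protocol and SAP*

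**What the plan says.** Section 5.1 (Sample Size Considerations) bases the TFV-DP power statement on 20 participants in each arm, a 5% type I error and a control rate of roughly 40% above the 700 fmol/punch threshold at 3 months. The claim is "using a chi-square test statistic, we have 80% power to detect a relative risk of 2.0 or larger". For 6 months it continues: "If we assume 30% adherence at 6 months, we have 80% power to detect a relative risk of 2.4 or higher". The relative risks are printed to one decimal. The section does not give the intervention-arm rates, the sidedness or the variance formula.

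The same section justifies the total of 80 by published recommendations for pilot studies. Section 2.6 lists TFV-DP adherence as a secondary outcome; feasibility and acceptability are primary. In Section 5.3 the TFV-DP comparison "between treatment arm will be estimated using chi-square or Fisher's exact test at both 3 and 6 months", with at least 20 per arm.

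**The concern.** Each sentence claims 80% power at a stated relative risk and at anything above it. That makes 2.0 and 2.4 the smallest effects for which the claim is made, and the claim has to hold at those values. For the test that 5.1 names, it does not.

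Little in this trial is at stake, because the sample size was not chosen to meet this target. However, Section 2.1 says that the pilot is meant to inform a later, more definitive trial. Readers who use 5.1 for that purpose should see the power that the named test has.

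**Working it through.** **Inputs.** From 5.1: n = 20 per arm, type I error 5%, target power 80%, control rates 0.40 and 0.30, RR 2.0 and 2.4. The intervention rates follow: 0.40 × 2.0 = 0.80 and 0.30 × 2.4 = 0.72. Allocation is 1:1 (5.2).

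**Assumptions.** The test is taken as two-sided, because a chi-square test on one degree of freedom rejects in either direction. The other power statement in 5.1, "we have 80% power to detect a difference in adherence scores of 12.7 units between the two groups", fits this: a two-sided t-test with 40 per arm, SD 20 and 80% power gives 12.69. No continuity correction is applied.

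**Step 1: reproduce the plan's figures.** With d = p2 − p1, p̄ = (p1 + p2)/2 and z = 1.960:

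- Pooled formula, which corresponds to the Pearson test: power = Φ{[d√n − z√(2p̄(1−p̄))] / √[p1(1−p1) + p2(1−p2)]}.
- Unpooled formula: power = Φ{d√n / √[p1(1−p1) + p2(1−p2)] − z}.

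Solving each for the RR that gives 80% power:

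| Control rate | Pooled | Unpooled | Printed in 5.1 |
|---|---|---|---|
| 40% | 2.049 | 1.993 | 2.0 |
| 30% | 2.433 | 2.350 | 2.4 |

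Both formulas agree with the printed values to one decimal.

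**Step 2: power at exactly the printed bounds, by formula.** √20 = 4.472.

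- 40% vs 80%, pooled: d√n = 1.789; z√(2 × 0.6 × 0.4) = 1.358; denominator √(0.24 + 0.16) = 0.632. Φ(0.431/0.632) = Φ(0.681) = 75.2%.
- 40% vs 80%, unpooled: Φ(1.789/0.632 − 1.960) = Φ(0.868) = 80.7%.
- 30% vs 72%, pooled: d√n = 1.878; z√(2 × 0.51 × 0.49) = 1.386; denominator √(0.21 + 0.2016) = 0.642. Φ(0.493/0.642) = Φ(0.768) = 77.9%.
- 30% vs 72%, unpooled: Φ(1.878/0.642 − 1.960) = Φ(0.968) = 83.3%.

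**Step 3: power of the named test without a variance approximation.** Sum the binomial probabilities over all 21 × 21 possible outcome tables in which the uncorrected Pearson statistic exceeds 3.841.

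- 40% vs 80%: 75.3%.
- 30% vs 72%: 76.0%.
- RR at which exact power reaches 80%: 2.045 and 2.462.

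The exact results agree with the pooled formula at 3 months and lie about 2 points below it at 6 months. The unpooled formula overstates the power of this test at both times.

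**Step 4: rates at which the claim holds.**

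| Rates | RR | Pooled | Exact |
|---|---|---|---|
| 40% vs 82% | 2.05 | 80.1% | 80.5% |
| 30% vs 73.5% | 2.45 | 81.1% | 79.3% |
| 30% vs 74% | 2.47 | 82.1% | 80.3% |

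At 6 months the exact calculation needs 74%, because 73.5% falls just short.

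**The case against.** The strongest reply is that nothing was miscalculated. Both common planning formulas give 2.0 and 2.4 at the precision printed. If the unpooled formula was used, power at those values comes out as 80.7% and 83.3%, so the author would have seen the target met. This stands as an account of how the figures may have arisen. It does not make the sentence right, because 5.1 names the chi-square test, and the exact power of that test requires no choice of formula.

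A second reply is that the gap lies within the uncertainty of the inputs. The 40% is given as approximate and the 30% as an assumption. At the printed RRs a control rate of 42% gives 81.0% pooled and 82.1% exact, and 31.5% gives 82.4% and 80.8%. In addition, 20 per arm is a minimum in 5.3, and 3.5 allows more than half of participants to be tested. By the pooled formula 23 per arm would reach 81.2% at RR 2.0, and 22 would reach 81.9% at RR 2.4. These facts soften the point. They do not remove it, because 5.1 ties its 80% to 20 per arm and to those control rates.

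A reader might infer that 5.1 computed 2.049 and 2.433 and rounded them down. The documents do not support that: neither value appears in them, and the unpooled values 1.993 and 2.350 round up to the same printed figures. A reader might also infer that the Fisher option in 5.3 makes the overstatement worse. But 5.1 makes its claim for the chi-square test only, and 5.3 does not commit to Fisher's test for every table.

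**Conclusion.** The statement is wrong as written, and the matter is minor. At the bounds given in 5.1 the named test has about 75% power at 3 months and about 76-78% at 6 months. The shortfall is about 5 points and 2 to 4 points respectively. This assumes a two-sided 5% Pearson chi-square without continuity correction, exactly 20 per arm, and control rates of exactly 40% and 30%.

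The cause is approximation or rounding and cannot be settled from the documents. It is not an error in the inputs. The size of the trial does not depend on it, since n=80 is justified separately and TFV-DP is a secondary outcome.

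**What to change.** Restate the TFV-DP power sentence in 5.1. Say that the test is two-sided, print the rates in both arms and name the method of calculation. Either of these would do:

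- About 80% power with 20 per arm for 40% vs 82% (RR 2.05) at 3 months and for 30% vs 74% (RR 2.47) at 6 months.
- Keep RR 2.0 and 2.4, and state power of about 75% for 40% vs 80% and about 76-78% for 30% vs 72%.

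The cost is an edit to one or two sentences. Enrollment, assays, visits and the analysis stay as they are.

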2.6. Outcomes

Primary Outcome

- Feasibility
- Acceptability

Secondary Outcomes

- Utilization of individual features of mobile intervention
- Adherence, self-report to PrEP
- Adherence, objective via tenofovir diphosphate (TFV-DP) levels in dried blood spots (in 50% of participants)
- Clinical visits for PrEP care

- Stigma-related barriers
- HIV seroconversion

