2.8. Participant Retention

Every attempt will be made to complete follow-up study procedures and data collection for all randomized participants. Our retention process will leverage the use of multiple contact methods - including telephone calls, text messages, e-mail reminders, and social media – and ask permission for the use of each.

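### The 12.7-unit detectable difference in self-reported adherence is 0.635 SD on the plan's own SD of 20, not about half an SD; power for half an SD is about 60%

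*Combined protocol and SAP*

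**What the plan says.** Section 5.1 (Sample Size Considerations) plans 40 participants per group, 80 in total, and says this size "is consistent with recommendations of sample sizes for pilot studies of this nature". It then gives power for two adherence outcomes. For the three-item self-report score, "prior research on ART therapy suggests a standard deviation of approximately 20". The plan carries that SD over to PrEP users, takes a type I error of 5%, and concludes that "we have 80% power to detect a difference in adherence scores of 12.7 units between the two groups". The next sentence interprets the figure: "This is approximately half of a standard deviation change, and should provide good preliminary evidence to inform future trials".

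Section 2.6 lists "Adherence, self-report to PrEP" among the secondary outcomes; the primary outcomes are feasibility and acceptability. Section 5.3 gives the analysis: "T-tests will compare the mean adherence score between intervention and control arm at 3 and 6 months", with permutation tests in addition.

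Section 5.1 makes no allowance for dropout. Section 2.8 sets the aim: "Every attempt will be made to complete follow-up study procedures and data collection for all randomized participants". No expected retention is stated. The retention bands in section 5.3 (for example "80-89% = acceptable feasibility") are criteria for judging feasibility and are not an input to the sample size.

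**The concern.** Three adjacent statements in section 5.1 do not agree. With an SD of 20, half an SD is 10 units, not 12.7. For 12.7 units to be half an SD, the SD would have to be 12.7/0.5 = 25.4, and the documents give no other SD for this score.

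The gap matters because a standardized effect is what a reader takes from a pilot. Someone told that the trial has 80% power for about half an SD credits it with a sensitivity it lacks, and could read a null result as evidence against a half-SD benefit. With 40 per arm, such a benefit would be missed about 40% of the time. Section 2.1 says the pilot exists to inform a later trial, and the faulty sentence makes the same claim for itself.

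**Working it through.** **Inputs**
- 40 per arm, SD 20, type I error 5%, 80% power (section 5.1).
- 1:1 allocation (section 5.2).
- Two-sample t-test (section 5.3).
- Sidedness is not stated. Two-sided is inferred because only a two-sided test reproduces 12.7.

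**1. Reproduce the plan's figure.** The standard error of the difference in means is 20 × √(2/40) = 4.472.
- Normal approximation: 4.472 × (1.960 + 0.842) = 12.53 units.
- Exact calculation (noncentral t, 78 degrees of freedom): 12.69 units, with 80.1% power at 12.7.
- One-sided 5%: 11.1 units (normal) or 11.2 (t), so not the plan's figure.

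The stated 12.7 units is therefore right for a two-sided test with all 40 per arm evaluable.

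**2. Standardize it.** 12.7/20 = 0.635 SD (0.634 before rounding to 12.7). This is 0.635/0.5 = 1.27 times the effect described. The detectable difference scales with the SD, so at 40 per arm the standardized value is about 0.63 whatever the true SD is.

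**3. Power at a true half-SD difference (10 units).** The noncentrality is 10/4.472 = 2.236.
- Normal approximation: Φ(2.236 − 1.960) = 60.9%.
- Noncentral t: 59.8%.
- One-sided 5%: 71.6% (t), still short of 80%. The one-sided detectable effect is 11.2/20 = 0.56 SD.

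**4. Size needed for 80% power at half an SD.** n per arm = 2 × (1.960 + 0.842)² / 0.5² = 62.8, so 63 by the normal approximation. The t-test needs 64 per arm, or 128 in total. Against 40 per arm that is 64/40 = 1.6 times as many.

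**5. Precision with complete follow-up.** The 95% confidence interval half-width for the mean difference is 1.991 × 4.472 = 8.9 units.

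**6. Retention, as illustration only.** The range below is borrowed from the section 5.3 feasibility bands and assumes equal loss in both arms. It is not a forecast.

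| Evaluable per arm | Detectable at 80% power | Power for 12.7 units | Power for half an SD |
|---|---|---|---|
| 40 (100%) | 12.7 units (0.63 SD) | 80% | 60% |
| 36 (90%) | 13.4 units (0.67 SD) | 76% | 55% |
| 32 (80%) | 14.2 units (0.71 SD) | 71% | 50% |
| 28 (70%) | 15.2 units (0.76 SD) | 65% | 45% |

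Small losses matter little: power for 12.7 units is 79% at 39 per arm and 78% at 38.

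**The case against.** The strongest reply is that this is a loose gloss on a correct calculation. The plan never claims 80% power for 10 units. The SD and the 12.7 units stand just before the phrase, so a careful reader can see the true ratio. Nothing depends on it: the sample size rests first on pilot recommendations, the primary outcomes do not use adherence, and no go/no-go rule is attached to this score. Nor do the documents say that a later trial will be sized from the half-SD label. The retention figures are not the sponsor's assumptions either.

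Much of this stands, and it limits the consequence. The 12.7 units is right, and enrollment, tests and decision rules are unaffected. The retention point is missing detail, not an arithmetic error. What does not stand is that the word approximately covers the gap. Calling 12.7 units about half an SD, directly after stating 80% power for it, tells the reader that the design has 80% power near half an SD, and the true figure there is about 60%. Doubt about the SD does not help, because the standardized effect at 40 per arm does not depend on it. A one-sided test does not help either.

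**Conclusion.** The description is wrong on the plan's own inputs. The detectable difference is 0.635 SD, and power for a half-SD difference is about 60%, about 20 percentage points below what the sentence implies. This assumes a two-sided 5% t-test and all 40 participants per arm evaluable; any loss to follow-up makes the sensitivity worse. The correction should be made because the sentence states a power property of the design and offers it as guidance for future trials. It gives no reason to question the 80 participants or the planned analyses.

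**What to change.** In section 5.1, delete the half-SD description. State instead that 12.7 units is about 0.635 of the assumed SD with complete follow-up (40 evaluable per arm), and that power for a half-SD (10-unit) difference is about 60%. Stating that the test is two-sided would remove the remaining ambiguity.

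A useful but optional addition is one sentence on attrition, labelled as an assumption. For example, if 80% were retained (32 per arm), the detectable difference would be 14.2 units (0.71 SD) and power for half an SD about 50%.

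The cost is one or two sentences and a less favourable stated sensitivity. Enrollment, tests and decision rules stay as they are.
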